5 STUDY PROCEDURES

The study design diagram is presented in [Figure 3](#) and the Schedule of Study Assessments and Procedures is presented [Appendix 1](#).

Figure 3 Study Design Diagram

5.1 Screening

Informed consent is to be obtained prior to the start of any protocol-specified assessments or procedures. However, some patients may complete cystoscopy with pathology assessment and/or urine cytology test as part of the standard of care prior to signing the informed consent. Those test results, if they are within 45 days prior to signing informed consent, could be part of eligibility assessment. In this case, there is no need to repeat same test procedure. The procedures and evaluations required for enrollment into the study are summarized below. All potential study patients will be screened and eligibility determined prior to enrollment. Screening assessments performed prior to the signing of informed consent as part of the site’s routine standard of practice will be allowed at the discretion of Spectrum. This information should be discussed with the Medical Monitor before the patient is randomized and enrolled in the study.

All procedures are to be performed as outlined in [Appendix 1](#) prior to the start of study treatment, unless otherwise noted. Screening includes a cystoscopic exam and urine cytology in order to assess the clinically apparent stage and grade of the bladder tumor. A cystoscopic or urine cytology exam conducted as part of the standard practice within 45 days prior to the signing of the informed consent may serve as the assessment as long as stage and grade of tumor are reported using the World Health Organization (WHO) 2004 grading system.

5.2 Patient Assignment

Confirmation of eligibility is to be received by the investigational site from Spectrum prior to enrollment of a patient. After a patient has signed the ICF, the Investigator or site staff should log into IWRS and obtain a Patient ID. The Patient ID will include two parts: the site number comprised of 5 digits with a 2-digit alphabetic country code [Reference ISO 3166] followed by a 3-digit site specific numeric code and a 3-digit patient sequential number, unique to a site, separated by a hyphen (ie, ██████████).

Once the Investigator or site staff have completed the required CRFs, and approval for randomization has been received from Spectrum, the site will randomize the patient using a pre-specified randomization scheme. Patients must not undergo TURBT until they have been randomized. Please refer to the study binder for detailed instructions regarding enrollment.

5.3 Timing of Assessments and Procedures

5.3.1 Screening

The following screening assessments should be performed within 30 days of Day 1 (Day -30 to Day -1).

- Informed Consent
- Urine cytology (Within 45 days prior to signing informed consent)
- Cystoscopic Exam (Within 45 days prior to signing informed consent)
- Complete medical history
- Vital signs (temperature, blood pressure, and heart rate)
- Demographic data
- Physical examination
- Height and weight
- Complete blood count (CBC)
- Chemistry
- Urine dipstick
- Pregnancy test (beta human chorionic gonadotropin [β -hCG]) in women of childbearing potential
- Adverse events using NCI CTCAE Version 4.03
- Concomitant Medications

5.3.2 Treatment Period: Visit 1 (Day 1)

If the screening assessments for the physical examination, hematology, chemistry, urine dipstick were performed within 3 days (72 hours) prior to Day 1/TURBT, these assessments do not need to be repeated at the Day 1 Visit.

- Vital signs (temperature, blood pressure, and heart rate)
- Complete blood count
- Chemistry
- Randomization
- Urine dipstick just prior to drug instillation
- TURBT and packaging of pathology specimens to be sent to local pathology
- Visual inspection for gross hematuria post-TURBT but prior to drug instillation
- Qapzola or placebo administration
- Concomitant Medications
- Adverse events using NCI CTCAE Version 4.03

5.3.3 Safety Follow-up Visit: Visit 2 (Day 35 [±5 days] post-TURBT (non-Target patient population) or Visit 3 (Month 3 Follow-up Visit) (Target patient population)

- Vital signs (temperature, blood pressure, and heart rate)
- Physical examination
- Complete blood count
- Chemistry
- Urine dipstick
- Adverse events using NCI CTCAE Version 4.03
- Concomitant medications

5.3.4 Long-Term Follow-up Visits - Visits 3 through 10 (First 2 Years: Every 3 months [±30 days] Post-TURBT) and Visits 11 through 16 (Years 3-5: Every 6 months [±60 days])

- Physical exam (required at Month 3 Follow-up Visit, as needed thereafter)
- Vital signs (temperature, blood pressure, and heart rate) (required at Month 3 Follow-up Visit, as needed thereafter)
- Urine dip stick prior to cystoscopy
- Complete blood count (Month 3 Follow-up Visit only)
- Chemistry (Month 3 Follow-up Visit only)
- Urine cytology
- Cystoscopy
- Only AEs related to study procedures will be recorded until the End-of-Study
- Concomitant medications (Intravesical treatment only)

- TURBT and packaging of pathology specimens to be sent to local pathology (if necessary)

5.4 Description of Study Assessments and Procedures

5.4.1 Explain Study and Obtain Written Informed Consent

Informed consent is to be obtained prior to the start of any protocol-specified assessments or procedures (including required washout of any prohibited medications). The Principal Investigator or designee is to discuss the study fully with the patient and obtain written Informed Consent. The written ICF is to be signed by the patient and the Principal Investigator or designee. A copy of the signed ICF is to be given to the patient.

5.4.2 Medical History

Medical history includes the history of the neoplastic disease, its symptoms, findings, previous therapy, and investigations as well as significant past and all co-existing diseases and current medications for the previous 5 years.

5.4.3 Review Inclusion/Exclusion Criteria

At Screening and prior to enrollment, the Inclusion and Exclusion Criteria will be reviewed by the Principal Investigator or other qualified healthcare professional to ensure that the patient qualifies for the study.

5.4.4 Physical Examination

A complete physical examination, including a description of external signs of the neoplastic disease and co-morbidities is performed at Screening and the Safety Follow-up/Month 3 Follow-up Visit. A physical examination is only performed at all other visits if it is deemed clinically necessary. Physical examinations are to be completed by a physician or other healthcare professional licensed to perform such examinations. Findings will be documented in the patient's medical record and on the appropriate CRF pages. Any abnormalities after enrollment are to be recorded on the AE CRF.

5.4.5 Vital Sign Assessments

Temperature, blood pressure, and heart rate are to be recorded at Screening, at the Treatment Visit, and the Safety Follow-up/Month 3 Follow-up Visit.

5.4.6 Clinical Laboratory Tests

A local laboratory will be used to process all clinical specimens. The following clinical laboratory parameters will be evaluated in this study:

- **CBC** - The results of the laboratory assessments should be evaluated and medically accepted by the responsible physician for the assessment of clinical significant abnormalities.
- **Chemistry Panel** - Comprehensive chemistry and electrolytes including BUN, creatinine, AST/SGOT, ALT/SGPT, alkaline phosphatase, and albumin. The results of

the laboratory assessments should be evaluated and medically accepted by the responsible physician for the assessment of clinical significant abnormalities.

- **Urinalysis** - Urinalysis will be performed using urine dipsticks.

5.4.7 Urine Cytology

Urine cytology will be obtained for all patients at Screening (or up to 45 days prior to signing of informed consent), Treatment Visit 1, every 3 months (± 30 days) (calculated from date of TURBT) for 2 years and then every 6 months (± 60 days) until either a confirmed tumor recurrence or the End-of-Study, whichever occurs first. At Screening, if a patient has a positive cytology for a malignancy, imaging of the upper genitourinary tract should be conducted to confirm that there is no upper tract malignancies. Imaging modality can include contrast CT, MRI, or ultrasound with retrograde pyelograms. If a patient is confirmed to have a disease of upper tract or prostatic urethra, the patient is considered not eligible for the study and no other study related procedures should take place.

Similarly, at any time point during the follow-up, if a patient has a positive cytology that cannot be explained by bladder findings or bladder pathology, imaging should be conducted to confirm that there are no upper tract malignancies and that the prostatic urethra is excluded as a reservoir.

5.4.8 Cystoscopy

Cystoscopy will be performed at Screening (or up to 45 days prior to signing of informed consent), every 3 months (± 30 days) from the date of TURBT for the first 2 years, and every 6 months (± 60 days) until either a confirmed tumor recurrence or the End-of-Study, whichever occurs first. An operative report should contain the number, size and location of the tumors. All lesions should be biopsied and sent for pathological review; recurrences are to be reported on the appropriate CRF. All clinical decisions will be made based on the local pathologist's report. All pathology reports must include the tumor stage and grade for each lesion removed.

5.4.9 TURBT

TURBT will be performed according to each site's standard operating procedure. An operative report should include number, size, and location of the tumors removed. The seven bladder regions are: dome, left and right lateral walls, anterior and posterior walls, trigone, and bladder neck. Each tumor/lesion resected during TURBT should be submitted to the local pathology lab in a separate container, noting the location, to ensure that the tumor stage and grade for each lesion is assessed. All histology specimens will be read by a local pathologist and all pathology reports must include the location, size, stage, and grade for each tumor/lesion removed according to the 2004 WHO/ISUP grading system along with the presence/absence of muscle fiber in the lesion.

Patients with significant complications from TURBT (ie, bladder perforation, ongoing bleeding) should not receive study drug. Within the administration window (60 ± 30 minutes post-TURBT), study drug administration should be delayed to allow for resolution of significant bleeding. If significant bleeding does not stop, decision to administer the drug should be left to the Study Investigator.

All clinical decisions will be made based on the local pathologist's report. Following study treatment on Day 1, pathology will be reviewed by the Study Investigator and if the patient's

tumor(s) is other than low- to intermediate-risk NMIBC, the patient will be discontinued from the study and return at Day 35 (± 5 days) for a Safety Follow-up Visit.

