3. Time to Disease Progression (based on the tumor stage)
4. Safety

SAFETY ASSESSMENTS:

Safety will be assessed by reported/elicited adverse events (AEs), laboratory test assessments, and physical examinations.

Safety Endpoints

- All AEs
- Treatment-related adverse events
- Serious Adverse Events (SAEs)
- AEs leading to discontinuation
- AEs of special interest (\geq grade 3 dysuria and hematuria)
- Vital signs (body temperature, blood pressure and heart rate) and routine laboratory test parameters (complete blood count and blood chemistry)
- Deaths

Adverse Event and Serious Adverse Event Reporting:

From the time the study Informed Consent is signed through the day of study drug administration, only SAEs that are related to study procedures are to be recorded. For all non-Target population patients, all adverse events from the time of study drug administration until Day 35 (± 5 days) post-TURBT will be recorded. For Target population patients, all adverse events will be recorded from the time of study drug administration until the 3-month Follow-up Visit. Only deaths and AEs related to study procedures will be recorded for the remainder of the follow-up period.

Independent Data Monitoring Committee (IDMC)

The safety of the 8 mg/50 mL Qapzola dose will be evaluated by an IDMC for the first 30 patients treated in the study. Continuation of the study at this dose level will be determined based on the IDMC evaluation. The IDMC is also responsible for the review of the unblinded futility analysis.

STATISTICAL METHODS:

The primary analysis population is the Target Population, which will consist of all patients with confirmed low-to-intermediate-risk NMIBC. The stage and grade determination for the Target Population will come from the pathology review. Tumors will be graded using 2004 WHO/ISUP criteria.

The Safety Population includes all patients who have had a TURBT and have received treatment of study drug (Qapzola or placebo).

The enrolled patients will be randomized in a 2:1 ratio to either Qapzola or placebo. The primary endpoint is Time to Recurrence in the Target Population. The primary endpoint analysis involves a test of comparison: 8 mg Qapzola vs. placebo using 2-sided log-rank test at 5% level of significance.

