Qapzola has been shown to be inactivated by red blood cells [12]. Hematuria, both microscopic and macroscopic, is the most common adverse event in the immediate post-TURBT period. Therefore, any bleeding in the post-operative period following TURBT could inactivate Qapzola following its immediate, postoperative instillation, reducing its efficacy. This provided the rationale for the further analysis of the Phase 3 study data for SPI-611 and SPI-612 based on the time interval of drug instillation post-TURBT (<30 minutes, 31 to 90 minutes, and >90 minutes). This analysis demonstrated a robust 20.3% reduction in the 2-Year Recurrence Rate in Qapzola-treated patients in the Ta, G1-G2 Population who received treatment 31 to 90 minutes after TURBT, compared to patients treated with placebo in the same time interval (23.3% vs 43.6%); this difference was statistically significant ($p=0.0346$), with the odds ratio (0.39; 95% CI 0.16, 0.94) in favor of Qapzola. Since the maximum benefit from intravesical instillation was seen in the group of patients receiving instillation at 31 to 90 minutes post-TURBT, this dosing window was selected for instillation of study drug (Qapzola or placebo) (60 ± 30 minutes post-TURBT) in the new proposed Phase 3 study.

A single instillation dose of 8 mg in 50 mL Qapzola was chosen as the study treatment in the current study. The 4 mg in 40 mL dose of Qapzola was established in the Phase 1 dose-escalation study and was used in the Phase 2 and previous Phase 3 studies. Based on the data from the Phase 1 dose-escalation study, it was found that the 8 mg in 40 mL dose (0.2 mg/mL) did not show any clinically relevant safety concerns. Because the 8 mg dose of Qapzola, at a concentration of 0.2 mg/mL, was determined to be safe, the dose of 8 mg in 50 mL (0.16 mg/mL) was chosen as the dose to be used in SPI-QAP-306. As part of the safety monitoring in the study, an Independent Data Monitoring Committee (IDMC) will review the unblinded safety data from the first 30 patients to verify that the 8 mg/50 mL dose is safe.

[figure not shown]

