6.2.2 Schedule of Study Drug Administration

A single dose of study drug on Day 1 is to be administered at 60 ± 30 minutes post-TURBT. Within the administration window (60 ± 30 minutes post TURBT), study drug administration should be delayed to allow for resolution of significant bleeding. Patients not candidates for post-operative intravesical chemotherapy after from TURBT (ie, extensive resection, bladder perforation, ongoing bleeding) should not receive study drug.

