6.2.2.2 Instillation of Study Drug

Following drainage, study drug is to be instilled into the bladder via a 100% Silicone Foley catheter at 60 ± 30 minutes post-TURBT. Adequate hemostasis should be obtained, and the urine should appear visually clear (No macroscopic evidence of bleeding) before study drug instillation. Within the administration window (60 ± 30 minutes post TURBT), study drug administration should be delayed to allow for resolution of significant bleeding. Patients with significant complications from TURBT (ie, bladder perforation, ongoing bleeding) should not receive study drug. The bladder should be emptied before instilling the study drug. The 50 mL of the study drug should be slowly instilled into the bladder taking care not to introduce air. When instillation is complete, the Foley catheter should be clamped for 60 minutes (± 5 minutes).

If during the retention period, there is any leakage around the catheter, the amount of study drug leaked should be estimated and recorded. After 60 minutes (± 5 minutes) of retention, the bladder contents should be drained and the drained bladder contents disposed of according to institutional policy. The institution's routine guidelines for the postoperative care should be followed.

No diuretics are allowed prior to instillation on the study drug instillation days. Study drug should not be instilled if a subclinical or clinical bladder perforation is suspected.

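### Protocol 5.4.9 bars dosing during ongoing bleeding, then lets the investigator dose if significant bleeding does not stop; 6.2.2 and 6.2.2.2 give no such discretion

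*Protocol*

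**What the plan says.** The second paragraph of Protocol 5.4.9 gives three instructions in a row.

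1. Patients with significant TURBT complications are not to be dosed. The complications are named: "ie, bladder perforation, ongoing bleeding) should not receive study drug".
2. Within the window of 60 ± 30 minutes after TURBT, dosing is to wait until significant bleeding has resolved.
3. "If significant bleeding does not stop, decision to administer the drug should be left to the Study Investigator."

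Protocol 6.2.2 repeats the second instruction ("study drug administration should be delayed to allow for resolution of significant bleeding"). It then lists reasons not to dose patients who are not candidates for postoperative intravesical chemotherapy: "ie, extensive resection, bladder perforation, ongoing bleeding) should not receive study drug". Protocol 6.2.2.2 repeats both rules, including "Patients with significant complications from TURBT (ie, bladder perforation, ongoing bleeding) should not receive study drug", and adds a condition for instillation: "Adequate hemostasis should be obtained, and the urine should appear visually clear (No macroscopic evidence of bleeding) before study drug instillation". Neither section contains the third instruction.

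Two other places assume that visible bleeding has been dealt with before dosing. Protocol 5.3.2 lists a visual check for gross hematuria between TURBT and instillation. Footnote f of the assessment schedule places the pre-instillation dipstick after gross hematuria has resolved. The SAP has no rule on bleeding.

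**The concern.** The discretion in 5.4.9 is discretion to give the drug, not to withhold it. It allows a cytotoxic agent to be instilled in a state that the rest of the protocol treats as a reason not to dose.

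The expected benefit is also doubtful in that state. Section 1.4 says that "any bleeding in the post-operative period following TURBT could inactivate Qapzola following its immediate, postoperative instillation, reducing its efficacy".

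Hematuria is a safety matter in this protocol. The Synopsis lists adverse events of special interest as those of at least "grade 3 dysuria and hematuria". Section 1.3.2 reports one Grade 3 hematuria SAE in the pivotal studies that was considered possibly related to Qapzola and began on the day of instillation. It also lists hematuria among the treatment-related SAEs after single instillations in the supportive studies.

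Two sites could therefore treat the same patient differently, each relying on protocol text. A monitor would have no stated basis for deciding whether dosing under 5.4.9 was a deviation.

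**Working it through.** The protocol states no figure on this point, so the check is a comparison of every instruction that bears on bleeding and dosing.

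| Place | Bleeding continues | Investigator may dose anyway? |
|---|---|---|
| 5.4.9, first instruction | Do not dose | Not stated |
| 5.4.9, second instruction | Wait, within the window | Not stated |
| 5.4.9, third instruction | Investigator decides | Yes |
| 6.2.2 | Wait; do not dose if ongoing | Not stated |
| 6.2.2.2 | Wait; do not dose if ongoing; clear urine needed first | Not stated |
| 5.3.2 and schedule footnote f | Check for gross hematuria; dipstick once it has resolved | Not stated |

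**Do the first and third instructions of 5.4.9 concern the same patient?** Yes. The first covers significant complications and names ongoing bleeding. The third covers bleeding that is significant and has not stopped. Treating *ongoing* and *significant* as different degrees does not separate them, because the third describes the more serious state.

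**Can the third instruction be met together with 6.2.2.2?** Only if the investigator decides not to dose. A bladder with unresolved significant bleeding does not meet the 6.2.2.2 requirement of no visible bleeding, so a decision to dose under 5.4.9 goes against 6.2.2.2.

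**Does the wording rank the rules?** No. The competing sentences all use *should*, and no text gives one section precedence.

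**When does the conflict arise?** The third instruction states no time. It follows the sentence on waiting within the window, so the natural reading is that it applies when the window ends:

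- Window: 60 − 30 = 30 minutes to 60 + 30 = 90 minutes.
- End of window: 90 minutes.

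**Is such dosing a listed deviation?** The per-protocol deviations in 8.5.5 include instillation outside 30 to 90 minutes. They do not name instillation during bleeding.

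**How many patients are affected?** The documents give no rate of persistent bleeding after TURBT, and none is assumed here.

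**The case against.** The strongest reply is that this is one stray sentence. Section 5.4.9 describes the resection, while 6.2.2.2 governs instillation. The Day 1 hematuria check and the dipstick footnote agree with 6.2.2.2, and withholding drug complies with every section. That is fair as a description of where the weight of the text lies, and it confirms that the discretion sentence is the outlier. It does not remove the sentence, which an investigator may follow as written.

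Other points limit the concern without overturning it.

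- **6.2.2 involves judgement.** Its bar is framed around whether a patient is a candidate for chemotherapy, and it adds extensive resection to the list. It still names ongoing bleeding and states no override.
- **The safety evidence is indirect.** None of the cited hematuria reports concerns instillation into a bladder already bleeding. Section 1.3.2 also says that adverse events were similar in both arms and that hematuria is expected after TURBT. The special-interest label is in the Synopsis but not in the endpoint lists of Protocol 8.6.1 or SAP 3.4.2.
- **Inactivation by blood is an efficacy argument.** It shows no safety harm. Its relevance is that the drug may do little for the patients to whom the discretion applies.
- **The 90-minute point is a reading.** If the discretion applies inside the window, it conflicts with the waiting rule as well. If it leads to dosing after the window, that dosing is also off schedule.

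Different handling between sites is possible but has not been shown.

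**Conclusion.** The inconsistency is real and can be established from the text alone. For a patient whose significant bleeding does not stop, 5.4.9 both bars dosing and permits it; 6.2.2 bars it, and 6.2.2.2 bars it and sets a condition that such a patient cannot meet. Nothing reconciles these instructions.

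The consequence is limited to dosing safety and consistent conduct. No effect on the hazard ratio, power or bias is claimed, no harm from the discretion is shown, and the number of affected patients is unknown. The SAP removed all efficacy objectives after early termination, so safety is the remaining objective and only these conduct and safety points bear on the study as it ended.

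The conclusion rests on two readings: that significant bleeding which has not stopped counts as ongoing bleeding, and that the discretion applies once the window has run out. The first is hard to avoid. The second affects only the stated timing, not the conflict. This should be fixed, because it changes who may receive a cytotoxic instillation while bleeding and the repair is simple.

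**What to change.** Delete the discretion sentence in 5.4.9. In its place, refer to the condition already in 6.2.2.2 (bleeding controlled, urine clear to the eye) and state that drug is withheld if the condition is not met by 90 minutes after TURBT. This adds no new threshold and makes the three sections agree.

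The change is one sentence. Its cost is that some randomised patients may go undosed, at a rate the documents do not give. Under Protocol 8.3, those with confirmed target pathology would stay in the Target Population and could slightly dilute the treatment effect. Those with non-target pathology leave the efficacy analysis in any case. For scale, Protocol 8.1 plans 284 Qapzola Target patients, so each undosed one is 1/284 = 0.0035, or 0.35% of that arm. With efficacy analyses removed by the SAP, this dilution bears only on the protocol's planned efficacy analysis.
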